9.7.2 Other Unanticipated Problems

Unanticipated problems are those involving risks to subjects or others and include any incident, experience, or outcome that meets **all** of the following criteria:

- Unexpected (in terms of nature, severity, or frequency) given (a) the research procedures that are described in the protocol-related documents, such as the WIRB-approved research protocol; and (b) the characteristics of the subject population being studied;

- Related or possibly related to participation in the research (in the guidance document, possibly related means there is a reasonable possibility that the incident, experience, or outcome may have been caused by the procedures involved in the research); and
- Suggests that the research places subjects or others at a greater risk of harm (including physical, psychological, economic, or social harm) than was previously known or recognized.

An incident, experience, or outcome that meets any of the three criteria above generally will warrant consideration of substantive changes or corrective actions in order to protect the safety, welfare, or rights of subjects or others.

Unanticipated problems noted by the site will be recorded and reported to the Principal Investigator within 24 hours of the site's awareness and to the WIRB per local reporting requirements.

9.8 Type and Duration of Follow-up of Subjects after Adverse Events

All adverse events will be followed until resolution or an appropriate endpoint is reached (e.g., the Medical Monitor attributes the adverse event to a cause other than the study drug or assesses it to be chronic or stable).

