5.8.1 Handling of Withdrawals

In the event of voluntary withdrawal from the study, a Premature Withdrawal (PW) Visit will be conducted to obtain a final caries exam and ensure that appropriate care under medical supervision is provided until the symptoms of any AE resolve or the subject's condition becomes stable or deemed chronic.

Reasonable effort should be made to contact any subject lost to follow up during the course of the study in order to complete study-related assessments and collect safety data.

Subjects who are withdrawn from the study will not be replaced.

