9.3 Adverse Events

An adverse event (AE) is any untoward medical occurrence associated with the use of a drug in humans, whether or not considered drug related. An AE can therefore be any unfavorable and unintended sign, symptom, or disease temporally associated with any use of a drug, whether or not related to the drug. An adverse event can arise from any use of the drug (e.g., off-label use, use in combination with another drug) and from any route of administration, formulation, or dose. This excludes minor fluctuations in signs or symptoms of the disease under study, but includes significant worsening of the disease. It also includes any apparently unrelated illness and any accident that occurs during participation in the study.

Some examples of adverse events are:

- Development of an illness during the study.
- Development of symptoms which may or may not be related to the use of a concomitant medication or investigational product.

All adverse events, whether observed by the Principal Investigator, elicited from or volunteered by the subject, subject's teacher or parent/guardian, should be recorded on the Adverse Event Log. This reporting will include a brief description of the event, the date of onset, the date of resolution, the duration and type of event, the severity, contributing factors, and any action taken with respect to the investigational product.

AEs occurring after informed consent is obtained but prior to randomization will be recorded as medical history, unless possibly related to a study procedure, in which case they will be recorded as adverse events in the case report form. New adverse events will be captured and reported on the AE log until 30 days following the last treatment or premature withdrawal, whichever comes first.

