9.6.3 Adverse Event Causality Definitions

For each adverse event, the relationship to the study drug (Medical Monitor's attribution of causality) must be recorded as one of the following on the Adverse Event Log:

TERM	DEFINITION	CLARIFICATION
Unrelated	No possible relationship	The temporal relationship between drug exposure and the adverse event onset/course is unreasonable or incompatible, or a causal relationship to study drug is implausible.
	Not reasonably related, although a causal relationship cannot be ruled out	While the temporal relationship between drug exposure and the adverse event onset/course does not preclude causality, there is a clear alternate cause that is more likely to have caused the adverse event than the study drug.
Possible	Causal relationship is uncertain	The temporal relationship between drug exposure and the adverse event onset/course is reasonable or unknown, dechallenge or rechallenge information is either unknown or equivocal, and while other potential causes may not exist, a causal relationship to the study drug does not appear probable.
Probable	High degree of certainty for causal relationship	The temporal relationship between drug exposure and the adverse event onset/course is reasonable. There is a clinically compatible response to dechallenge (rechallenge is not required), and other causes have been eliminated or are unlikely.
Definite	Causal relationship is certain	The temporal relationship between drug exposure and the adverse event onset/course is reasonable, there is a clinically compatible response to dechallenge, other causes have been eliminated, and the event must be definitive pharmacologically or phenomenologically, using a satisfactory rechallenge procedure if necessary.

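### Section 9.8 lets data collection on an open adverse event end on a non-drug attribution alone, which does not fit sections 9.3 and 9.6.3

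*Combined protocol and SAP*

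**What the plan says.** Section 9.8 states the general rule: "All adverse events will be followed until resolution or an appropriate endpoint is reached". It illustrates an endpoint other than resolution by two alternatives joined by *or*: "the Medical Monitor attributes the adverse event to a cause other than the study drug or assesses it to be chronic or stable".

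Section 9.3 covers events regardless of cause. Of the definition of an adverse event it says: "It also includes any apparently unrelated illness and any accident that occurs during participation in the study". The log entry for each event is to include "the date of onset, the date of resolution, the duration and type of event, the severity, contributing factors". The same section limits the capture of new events: "New adverse events will be captured and reported on the AE log until 30 days following the last treatment or premature withdrawal". That limit does not say how long an event already open is followed, so 9.8 is the governing text for open events.

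Section 9.6.3 defines the causality grades that the Medical Monitor assigns. Between Unrelated and Possible stands a grade defined as "Not reasonably related, although a causal relationship cannot be ruled out", for events with a clear and more likely alternate cause. (Its row label is missing in the text available to me; the list in 9.6.2 suggests that it is the unlikely-related grade.)

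Section 11.3.2 plans tables of events by arm, severity and judged relationship. It also plans Fisher's exact tests on whether a child had at least one event, repeated without mild symptoms.

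**The concern.** Under 9.8 the causality judgement can decide whether the evidence that might change that judgement is collected. The judgement can also come early. Section 9.6.2 wants the Medical Monitor's assessment in the report of a serious event due within 24 hours of the site's awareness, so for such an event the exit could be met within a day.

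Adverse events are the only safety parameter listed in 9.1, and documenting safety is a secondary objective. Section 9.4 names thyroid problems as a risk of iodine. The phase 1 experience described in 2.1 is 12 children, with oral findings reported immediately and within 24 to 48 hours. A slow or recurring effect would therefore have to show itself through adverse event follow-up in this trial. An event put down to another illness and closed while still open is the kind of record in which such a pattern could be missed.

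**Working it through.** No arithmetic applies: the point concerns a text rule, and the documents give no adverse event rates. The check is to read 9.8 against the sections that it touches.

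1. **Is attribution sufficient by itself?** Yes. The two endpoints in 9.8 are alternatives, so an event attributed elsewhere need not also be stable or chronic. The rule covers all adverse events, sets no minimum period and makes no exception for serious ones. It is worded as an example, but a named example still permits the practice.

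2. **Against 9.3.** Resolution date and duration are log items for events of any cause. An event closed on attribution while open has neither. An event closed as chronic or stable also lacks a resolution date, but there the closure reason tells the reader how the event stood. After an attribution exit, the blank could mean resolved, persisting or worse.

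3. **Against 9.6.3.** The grades rest on the timing and course of the event and, from Possible upward, on dechallenge or rechallenge information. Course and dechallenge are observed after onset, and often after a first judgement. The grade quoted above has a more likely alternate cause but keeps the drug in play. Section 9.8 does not refer to the grades, so it is unclear whether that grade triggers the exit or only Unrelated does.

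4. **Can an attribution be revised later?** The Medical Monitor reviews events monthly (9.2). The assistant reviews and records them at visits 2 to 8 (7.3). The status of unresolved events is logged at withdrawal and unscheduled visits, without regard to attribution (7.5, 7.6). The written report of a serious event carries the Medical Monitor's current opinion on causality (9.6.2). Nothing forbids revision. For non-serious events, however, no section sets out a step at which causality is reconsidered, and a reviewer has less to go on once follow-up has ended.

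5. **What is kept and what may be missing?** Kept: occurrence, type, onset and initial severity. Possibly missing: resolution date, duration, later worsening and a revised causality grade.

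6. **Which analyses in 11.3.2 use the missing items?**
   - Fisher's exact tests on at least one event: occurrence only, so not affected.
   - The repeat without mild symptoms: affected if an event logged as mild worsened after closure.
   - Tables by severity and by relationship: affected by missed worsening and by unrevised causality.

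**The case against.** The strongest reply is that the protocol keeps several later looks at adverse events, listed in step 4. In addition, the teacher is contacted 48 hours after each treatment (7.4), and post-treatment hives or rash must reach the Principal Investigator within 24 hours whatever the suspected cause (9.6.1). This stands, and it defeats some stronger readings.

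- A reader might infer that an early attribution can never be corrected. The documents do not support that: no section freezes an attribution, and the reviews leave room for change. What remains is the absence of a written step for non-serious events.
- A reader might take 5.8.1 as a contradictory closure rule, because it provides that "appropriate care under medical supervision is provided until the symptoms of any AE resolve" or the condition becomes stable or chronic, with no exit on attribution. But 5.8.1 concerns the care of withdrawn children, not the closing of log entries. The difference in scope is worth noting and is not a contradiction.
- A reader might say that 9.3 guarantees a resolution date for every event. It lists log items and sets no length of follow-up, and events closed as chronic or stable cannot meet such a guarantee.
- A reader might infer that the safety comparison between arms is biased. The main tests count occurrence, so an excess in either arm is counted however it is attributed.

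Two further objections have some weight. Section 2.2.1 calls thyroid problems rare and very unlikely at the amount used, so the slow-effect scenario is a possibility and not a forecast. Closure conventions may also stand in the data management or safety monitoring plans (14.1, 14.4), which are not among these documents. Neither changes what 9.8 permits as written.

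**Conclusion.** The concern holds in a limited form. Section 9.8 makes non-drug attribution a sufficient reason to end follow-up of any adverse event, serious or not, while the event is unresolved and not stable. That is inconsistent with the items that 9.3 asks for and with the way 9.6.3 grades causality.

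The consequence is incomplete data on one subset: events still open when they are attributed elsewhere. It reaches the severity and relatedness tabulations and the repeat comparison without mild events, and it leaves the main occurrence tests untouched. Its size cannot be given. The documents state neither how many events will be attributed elsewhere nor how many of those will still be open. The share attributed to intercurrent illness would overstate it, because events that resolve before attribution lose nothing.

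The conclusion assumes that 9.8 is applied as written and that no unseen plan overrides it. It does not depend on which 9.6.3 grades trigger the exit, though the wider reading enlarges the subset. The change is worth making because it is short and improves the completeness of the safety record.

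**What to change.** Reconcile 9.8 with 9.3 and 9.6.3 on three points of data collection:

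- Attribution to another cause should not by itself end data collection on an open event. Its status is recorded until it is resolved, stable or chronic, through the existing visit reviews and the AE Follow-Up Log.
- The Medical Monitor confirms or updates the causality grade when the event closes, for non-serious as well as serious events.
- If any exit on attribution is kept, 9.8 should say which 9.6.3 grades it covers, and the log should show the event's status at closure.

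This concerns what is recorded and leaves treatment unchanged. The edit to 9.8 is about one sentence, plus a line on confirming causality. Unrelated events will stay open longer on the log. Section 7.3 lists no scheduled visit after visit 8, so a few events still open then would need a further contact.

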9.9 Halting Rules

Adverse events, particularly serious adverse events such as deaths and hospitalizations, will be carefully considered by the Sponsor. If necessary, the Sponsor will halt the study.

10. Site Monitoring

10.1 Clinical Site Monitoring

To ensure compliance with Good Clinical Practice (GCP) and other applicable regulatory requirements, the Regulatory Monitor ([name]) is responsible for monitoring to ensure the site is conducting the study according to the protocol, Standard Operating Procedures (SOPs), and other written instructions and regulatory guidelines. Monitoring visits by a Regulatory Monitor will be arranged in advance, at a mutually-acceptable time, with site personnel.

The site personnel must allow sufficient time for the Regulatory Monitor to review CRFs and relevant source documents, including access to electronic medical records, and address data queries.

The Investigators should be available to answer questions or resolve data clarifications. The monitoring plan will include written procedures for periodic and closeout monitoring visit activities, documentation and communication of visit findings, and maintenance of the record of on-site visits. The monitoring plan will serve as a guide to ensure standardization of study-specific procedures for the Regulatory Monitor who is responsible for ongoing quality review.

10.2 Regulatory Inspections

During the course of the study and after it has been completed, it is possible that one or more study site visits will be undertaken by authorized representatives of the Sponsor, WIRB, or regulatory agencies, such as the Food and Drug Administration (FDA). These audits may take place at any time during or after the study and are based on the local regulations, as well as ICH guidelines.

The purpose of the audit is to determine whether or not the study is being, or has been, conducted and monitored in compliance with the protocol as well as recognized GCP guidelines and regulations. These audits will also increase the likelihood that the study data and all other study documentation can withstand a subsequent regulatory authority inspection.

If such audits are to occur, they will be arranged for a reasonable and agreed-upon time.

11. Statistical Considerations

11.1 Study Hypotheses

The hypothesis is that the test varnish will be superior to the control varnish and will not be inferior in patient response to the control varnish. Also, there will be no difference in the frequency of adverse events.

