A phase 1 study of the safety of the new varnish was conducted in 12 healthy children with an average age of 47.6 months (WIRB PRO NUM: 20160539). No child evidenced any intra oral erythema or secondary changes as a consequence of the varnish application either immediately or within 24-48 hours post application. Neither were there any adverse effects. The FDA has reviewed the previous safety work and this protocol and issued IND 128835 for this work. The basic dental varnish formula was previously cleared by the FDA as a medical device and is currently on the market. To our knowledge there have been no adverse event reports on this varnish and it has never been withdrawn from the market. Povidone iodine is widely used in children in medicine. It has been used for intraoral application for many years without problems. Dental NaF varnish and povidone iodine have been applied sequentially at the same patient visit by clinicians for some time and two cohort studies have been published with no reports of harms.

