3.1 Study Objectives

Primary Objective:

To determine if Advantage Anti-Caries Varnish (test varnish) is superior to a control varnish containing only fluoride in the prevention of new caries lesions.

Secondary objectives:

- a) To establish that the response of child participants to the test varnish was not inferior to the control varnish
- b) To document the safety of the test varnish.

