4.1 Rationale for Study Design

The hypothesis is that the test varnish will be superior to the control varnish and will not be inferior in patient response than the control varnish. There will be no difference in the frequency of adverse events.

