11.3 Statistical Analysis Plan

11.3.1 Primary Statistical Analysis.

The primary analysis will be conducted in accordance with the intention-to-treat principle, and multiple imputation procedures will be used to account for missing caries information (Schafer, 1997). For the primary outcome, incremental dental caries based on d₂₋₃mfs/DMFS, the unit of analysis will be the child and the mean dental caries increment will be compared between the two interventions separately at 1 and 2 years post baseline using a two-sample t test assuming unequal variances. This approach assumes the distribution of dental caries increment is approximately symmetrical, which is often true in high-risk caries populations. In this case, non-symmetry, log-linear regression using robust standard errors, which can accommodate count outcomes with skewed distribution, will be used to compare the caries rates between the two interventions (Hardin & Hilbe, 2003). Covariate-adjusted linear (or log-linear) regression models using robust standard errors will be used to compare dental caries increment, adjusting for baseline dental caries, stratification variables (education center and school), gender and age of the participant (Hardin and Hilbe, 2003). Analyses will be performed using R (The R Foundation for Statistical Computing, 2016; Version 3.3.0) and SAS (SAS Institute, Cary, NC, Version 9.4).

11.3.2 Analysis of Safety Data.

Adverse events (AEs) will be tabulated by treatment group, severity, and perceived relationship to investigational product. For each AE, treatment group comparisons regarding the occurrence of at least one event will be made using Fisher's exact tests. The comparisons will be repeated excluding all mild symptoms. Similar analyses will be performed after grouping AEs by body system using standard Medical Dictionary for Regulatory Activities (MedDRA) coding. Individual AEs will be listed, with particular attention paid to serious AEs.

11.3.3 Participant Disposition.

The frequency and reasons for withdrawal will be summarized by treatment group, as will the number of missed visits and missed treatment applications (compliance).

12. Source Documents and Access to Source Data/Documents

The site will maintain appropriate medical and research records for this trial, in compliance with ICH E6, Section 4.9 and regulatory and institutional requirements for the protection of confidentiality of subjects.

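### The hypothesis of no difference in adverse event frequency is paired only with Fisher's exact tests, which can reject it but cannot support it; no margin, risk difference or confidence interval is planned

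*Combined protocol and SAP*

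**What the plan says.** Section 4.1 states: "There will be no difference in the frequency of adverse events". Section 11.1, under the heading of study hypotheses, repeats it: "Also, there will be no difference in the frequency of adverse events". The corresponding objective, secondary objective (b) in section 3.1, is more modest: "To document the safety of the test varnish". Adverse event occurrence is a secondary outcome in section 3.2.2.

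The analysis is in section 11.3.2. It begins descriptively: "Adverse events (AEs) will be tabulated by treatment group, severity, and perceived relationship to investigational product". The inferential part is: "For each AE, treatment group comparisons regarding the occurrence of at least one event will be made using Fisher's exact tests". Then: "The comparisons will be repeated excluding all mild symptoms". The same analyses are planned by MedDRA body system, and individual events will be listed with attention to serious ones.

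The documents give no acceptable difference, no risk difference or confidence interval for adverse events, no expected event rate, no significance level for the Fisher tests and no power for safety.

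**The concern.** Fisher's exact test takes equal event probabilities as its null hypothesis, and that is what sections 4.1 and 11.1 put forward as the trial's hypothesis. A small p-value would count against it. A large p-value would show only that the data do not contradict it, which also happens when a real difference exists and the trial is too small to show it. To support a claim of little or no difference, the plan needs an interval for the difference, and a margin if the claim is to be confirmatory. It has neither.

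The safety conclusion is at stake. For the combined varnish itself, section 2.1 cites one earlier study, a phase 1 study in 12 children ("Neither were there any adverse effects"). This trial adds a concurrent control and repeated applications for up to 24 months, so its adverse event comparison will carry weight. Some reportable events in section 9.6.1, such as hives, facial swelling and breathing difficulty, are plausibly uncommon, and that is where the planned tests are least informative.

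**Working it through.** **Inputs**
- Children per arm: section 11.2 gives 280 in total, so 280/2 = 140. Section 5.1 gives up to 600, half to each arm, so 600/2 = 300. Both are carried through because the sections disagree.
- Test: Fisher's exact, on children with at least one event (section 11.3.2).
- Significance level: not stated. Assumed two-sided 0.05 without multiplicity adjustment.
- Event rates: not stated. Assumed, with a range shown.

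The plan has no safety power or precision figure to reproduce.

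**Step 1: exact power.** For true rates p1 and p2 and n per arm, power is the sum over all pairs (x, y) of Bin(x; n, p1) × Bin(y; n, p2), counting only pairs whose two-sided Fisher p-value is at most 0.05.

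| Assumed rates | 140 per arm | 300 per arm |
|---|---|---|
| 1% v 3% | 8% | 31% |
| 2% v 5% | 16% | 45% |
| 5% v 10% | 27% | 59% |
| 10% v 20% | 59% | 92% |
| 20% v 40% | 95% | over 99% |

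A true doubling from 5% to 10% would be missed in 100 − 27 = 73% of trials at 140 per arm, and in 100 − 59 = 41% at 300 per arm.

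**Step 2: a concrete result.** Suppose 5 children have an event on test varnish and none on control. The two-sided Fisher p-value is 2 × C(n,5)/C(2n,5), which is 0.060 at n = 140 and 0.061 at n = 300. Neither is significant; six against none is needed at either size (p = 0.030). At 140 per arm, 5 v 0 is an observed difference of 5/140 = 3.6 points, and the Newcombe 95% interval runs from about 0.2 to 8.1 points. The planned output would give the counts and a non-significant p-value, but not that interval.

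**Step 3: what an interval would show.** If both arms truly had rate p, the approximate 95% half-width for the risk difference is 1.96 × √(2p(1 − p)/n).
- p = 5%, n = 140: 1.96 × √(0.095/140) = 5.1 points. At n = 300: 3.5 points.
- p = 2%: 3.3 and 2.2 points.
- p = 10%: 7.0 and 4.8 points.

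**Step 4: what a formal claim would need.** To rule out an excess of d with one-sided 0.025 and 80% power when both rates are p, n per arm = (1.960 + 0.842)² × 2p(1 − p)/d². With p = 5% and an illustrative d of 5 points, 7.85 × 0.095/0.0025 ≈ 298.3, so 299 per arm. That just fits 300 per arm with no allowance for loss, and does not fit 140.

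**The case against.** A reader might infer that the plan will declare the varnishes equally safe whenever the Fisher tests are non-significant. The documents do not support that. Section 11.3.2 gives no rule for interpreting the p-values and does not link them to the hypothesis. Objective (b) asks only that safety be documented, whereas objective (a), on child response, is worded as something to be established. The sentence in sections 4.1 and 11.1 can be read as an expectation. This stands, and it limits the point to a mismatch that invites a wrong conclusion.

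A reader might also infer that power is very low throughout. That is not supported either. The documents give no event rates, and the adverse event definition in section 9.3 takes in unrelated illness and accidents over up to two years in young children, so the proportion with any event could be well above 5%. For 10% v 20%, power is 59% or 92%. This stands too: the low figures apply to uncommon events and are worse at the smaller sample size.

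Finally, tables by arm are planned, so a reader could compute an interval from the counts, and section 9.2 provides monthly medical review. Neither removes the mismatch. Tables and listings do not quantify uncertainty in the difference, and even a well-powered non-significant test would not establish no difference without an interval or margin.

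**Conclusion.** The point holds as a mismatch between hypothesis and method. Sections 4.1 and 11.1 state no difference as a hypothesis, and the only planned inference can contradict it but not support it. This part follows from the text and needs no assumed rate.

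Its practical size depends on event rates the documents do not give and on which enrolment figure applies. Under two-sided 0.05, power for differences between rates of 10% or less, as tabulated, is 8% to 27% at 140 per arm and 31% to 59% at 300 per arm, so non-significance would say little about uncommon events. For common events with large differences the tests are reasonably sensitive, more so at 300 per arm. The primary endpoint, sample size and data collection are unaffected.

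**What to change.** 1. In sections 4.1 and 11.1, replace the statement that there will be no difference with one that the difference in adverse event frequency will be estimated.
2. In section 11.3.2, report the risk difference (children with at least one event) with a 95% confidence interval, for example Newcombe or Miettinen-Nurminen, for: any adverse event, any excluding mild, treatment-related events, serious events, and the section 9.6.1 reportable events.
3. Keep the Fisher p-values as descriptive, and state that non-significance will not be taken as evidence of equal safety. With very few events the interval and the p-value can fall on different sides of the conventional threshold, as in the 5 v 0 example, so the text should say that interpretation rests on the interval.
4. If the sponsor wants a formal claim of comparable safety, it should prespecify a margin with its justification and check it against the sample size that applies.

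Items 1 to 3 use data already being collected. They cost some wording and a few table columns, and the resulting safety statement will be less favourable than one of no difference.
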